### 438       **3.2.2 Procedures at Study Visits**

439 The following procedures will be performed at each visit, unless otherwise specified:

- 440       • Review of study device data
- 441       • Assessment of compliance with study device use by review of any available device data
- 442       • Assessment of device issues that have occurred
- 443       • Assessment of adverse events, using open ended questions to capture hyperglycemic and  
444       hypoglycemic events, and their underlying cause and relationship to the study device, study  
445       insulin or other parts of the system (such as the infusion set).
- 446       • A focused physical exam to include skin and infusion sites will be performed at each in person  
447       visit.
- 448       • Completion of a detailed case report form with respect to any infusion site reactions that have  
449       occurred.

450 At 13 weeks, the following additional procedures will be performed:

- 451       • Blood draw (venipuncture or fingerstick) for HbA1c measurement at central lab (13 weeks only)
- 452       • Completion of the following PRO surveys by the participant (age 14+) or parent: TRIM-D,  
453       Trim-DD (Diabetes Device), ITSQ (Insulin Treatment Satisfaction Questionnaire)

### 454       **3.2.3 Unscheduled Visits**

455 Participants may have unscheduled visits during the study period if required for additional device training  
456 or other unanticipated needs per the study investigator discretion.

## 457       **3.3 Exercise and Meal Challenges**

458 Participants will complete 3 meal and 3 exercise challenges during Lyumjev use. Procedures are  
459 described in section 5.1.

## 460       **3.4 Early Discontinuation of Study Device**

461 Participants who discontinue the study device prior to 13 weeks, either by choice or by investigator  
462 decision, will be asked to come for an end of study visit and then will be dropped from the study.  
463 If the visit occurs at 6 weeks or after, blood will be drawn for the central-lab HbA1c measurement and  
464 the PROs will be completed.

465

## Chapter 4: Study Devices and Drugs

466

### 4.1 Study Devices

468 The investigational device (CLC system) includes an insulin pump and a continuous glucose monitor.

#### 4.1.1 Insulin Pump

470 The study system will include the Tandem t:slim X2 with Control-IQ technology.

#### 4.1.2 Continuous Glucose Monitoring

472 The study CGM that is part of the CLC system is the Dexcom G6, which includes a transmitter and  
473 sensors. The CGM sensor will be replaced at least once every 10 days.

#### 4.1.3 Blood Glucose Meter

475 The study blood glucose meter is the Contour® NEXT (Ascencia Diabetes Care).

476 Blood glucose levels will be measured using the study's blood glucose meter (glucometer) and the  
477 CGM device will be calibrated if needed using the study glucometer and strips in accordance with the  
478 manufacturer's labeling.

#### 4.1.4 Ketone Meter

480 The study blood ketone meter is the Precision Xtra Blood Glucose and Ketone Monitoring System  
481 (Abbott Diabetes Care ).

482 Blood ketone levels will be measured when needed to evaluate prolonged hyperglycemia. The blood  
483 glucose meter component of the Precision Xtra device will not be used.

### 4.2 Study Drug

485 The study drug is Lyumjev (insulin lispro-aabc). The drug is a formulation of insulin lispro that includes  
486 the addition of two excipients, treprostinil and sodium citrate. Treprostinil enhances absorption by local  
487 vasodilatation without eliciting a systemic effect while citrate further enhances the speed of absorption.

#### • Acquisition

489 Study drug will be shipped by Eli Lilly to the study's central pharmacy for distribution to the  
490 clinical sites.

#### • Formulation, Appearance, Packaging, and Labeling

492 LYUMJEV (insulin lispro-aabc) injection is a sterile, aqueous, clear, and colorless solution for  
493 subcutaneous or intravenous administration. Each mL of LYUMJEV U-100 contains 100 units of  
494 insulin lispro-aabc and the inactive ingredients: glycerol (12.1 mg), magnesium chloride  
495 hexahydrate (1.02 mg), metacresol (3.15 mg), sodium citrate dihydrate (4.41 mg), treprostinil  
496 sodium (1.06 mcg), zinc oxide (content adjusted to provide 39 mcg zinc ion), and Water for  
497 Injection, USP.

#### • Product Storage and Stability

499 Dispense in the original sealed carton with the enclosed Instructions for Use.

500 Refrigerate unopened LYUMJEV vials between 36°F to 46°F (2°C to 8°C) until time of use and  
501 keep in the original carton to protect from light. Do not freeze or use LYUMJEV if it has been

502 frozen. Do not expose to direct heat. Discard opened or unopened LYUMJEV vials stored at  
503 room temperature below 86°F (30°C) after 28 days.

504 Change the LYUMJEV U-100 in the pump reservoir at least every 9 days, or according to the  
505 pump user manual, whichever is shorter, or after exposure to temperatures that exceed 98.6°F  
506 (37°C).

507

	Not in-use (Unopened)		In-use (Opened)	
	Room Temperature (below 86 F [30 C])	Refrigerated (36 F to 46 F [2 C to 8 C])	Room Temperature (below 86 F [30 C])	Refrigerated (36 F to 46 F [2 C to 8 C])
10 mL vial a,b	28 days	Until expiration date	28 days	28 days

508 a In-use (opened) vials, whether or not refrigerated, must be used within 28 days.

509 b When stored at room temperature, LYUMJEV can only be used for a total of 28 days including  
510 both not in-use (unopened) and in-use (opened) storage time.

511

### 512 **4.3 Study Device and Drug Accountability Procedures**

513 Device and drug accountability procedures will be detailed in the clinical center procedures manual.

### 514 **4.4 Participant Access to Study Device at Study Closure**

515 Participants will return all investigational study devices and supplies (insulin pump, CGM and related  
516 supplies, and unused insulin) at their final visit. Participant may keep the study ketone meter and study  
517 glucometer if these devices are not marked for investigational use only.

## Chapter 5: Testing Procedures and Questionnaires

518

### 5.1 Meal and Exercise Challenges

520 Participants will complete 1 missed meal bolus and 1 exercise challenge during the Humalog lead-in  
521 period, then 3 meal and 3 exercise challenges during Lyumjev use.

522 A minimum of 48 hours will occur between all challenges for each participant.

523 Participants will be instructed to communicate with study staff within one day prior to each challenge to  
524 review procedures and to have a contact with study staff after the completion of each challenge.

#### 5.1.1 Meal Challenges

526 The same meal should be used for each of the four meal challenges—either lunch or dinner (participant  
527 choice).

528 For the lead-in phase meal challenge, no bolus will be given for the meal.

529 During Lyumjev use, the three meal challenges will consist of:

- 530 • No bolus for the meal
- 531 • 50% bolus - calculate the bolus dose using the bolus calculator, and deliver half the  
532 recommended dose of insulin.
- 533 • Full bolus for the meal based on calculated bolus dose using the bolus calculator.

534 For each meal challenge, participants will:

- 535 1. Be in a fasting state for two hours prior to consuming the meal and the last manual insulin bolus  
536 more than two hours ago.
- 537 2. Only begin the meal challenge if the glucose is between 70 mg/dL and 200 mg/dL. *Subjects with*  
538 *hyperglycemia > 200mg/dL will reschedule their challenge for another time. If < 70 mg/dL,*  
539 *carbohydrate treatment can be given and then continue.*
- 540 3. Consume at least 50 grams carbohydrate for the meal. *Each participant will use the same meal*  
541 *for all of their meal challenges in the study. Participants will be encouraged to use the same*  
542 *frozen entrée of their choice for consistency.*
- 543 4. Write down the start and end time of eating the meal, as well as the meal content (to include  
544 amount of carbohydrate, protein and fat) on the study provided logbook.
- 545 5. Not give an additional bolus for up to 3 hours after the meal challenge, unless BG is above 300  
546 mg/dL for more than 1 hour, or symptoms of hyperglycemia develop.
- 547 6. Not take additional carbohydrates for up to 3 hours after the meal challenge, unless BG is < 70  
548 mg/dL, or symptoms of hypoglycemia develop.
- 549 7. Not exercise for 3 hours after the meal challenge.

550 For pediatric participants, caregivers/parents will be instructed to:

- 551 • Be physically present with the participant and monitor CGM glucose during the 3 hours of  
552 each meal bolus challenge timeline.
- 553 • Follow the study hypoglycemia and hyperglycemia safety guidelines, as well as the above  
554 guidelines for the challenge.

- 555           • Be in same residence with the participant for the overnight period after the challenges and to  
556           continue to monitor the participant.

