#### 3.1.1 Training on System Use

334 All participants will receive study system training from a qualified trainer. Since all of the participants  
335 will be experienced Control-IQ users, the amount of training will be customized for each participant.  
336 For pediatric participants, a parent (or legal guardian) will be required to attend the training procedures.

337 At a minimum training will include the following:

- 338 • Calibration of the CGM in accordance with manufacturer labeling
- 339 • Use of Lyumjev in the study pump
- 340 • Procedures for treating severe hypoglycemia
- 341 • Procedures for identifying potential infusion set failure and steps to take including the checking  
342 of the blood ketone level and changing the infusion set

343 The participant will be given a User Guide as a reference as well as Hypoglycemia and Hyperglycemia  
344 Guidelines.

345 Participants will be instructed to download the study device prior to each phone contact or office visit.

346 The participant will be instructed to use the system in closed-loop mode except 1) when no calibrated  
347 CGM sensor is available or 2) if insulin is delivered by any means other than the study pump (e.g.  
348 injection of subcutaneous insulin via syringe in the event of infusion site failure). If insulin is delivered  
349 by any means other than the study pump, participant will be instructed to turn off Control-IQ for four  
350 hours.

351 The participant will also be instructed to contact study staff during periods of illness with an elevated  
352 temperature >101.5 degrees Fahrenheit (38.6 degrees Celsius), periods of significant illness, or during  
353 periods of use of medications such as epinephrine for the emergency treatment of a severe allergic  
354 reaction or asthma attack in addition to use of oral or injectable glucocorticoids to determine if closed-  
355 loop use should be temporarily discontinued.

356 Participants will be provided with contact information and will be asked to call the study clinical staff  
357 for any health-related issues and for technical issues with the system. Participants may use the study  
358 pump without Control-IQ activated and study CGM during periods of component disconnections or  
359 technical difficulties.

360 Adult participants may use available manufacturer-provided CGM software and features of the study  

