### 386 **3.1.3 Training on Management of Hyperglycemia**

387 The t:slim X2 with Control-IQ system will issue a predictive hyperglycemia alert (Control-IQ High Alert)  
388 when the system has increased insulin delivery, but detects a CGM value above 200 mg/dL and does not  
389 predict the value will decrease in the next 30 minutes. During the course of the study, participants will be  
390 permitted to change the CGM high glucose threshold alert setting on their device or mobile app, but will  
391 be instructed to choose a value no greater than 300 mg/dL.

392 If the participant receives a Control-IQ High Alert, a prompt appears on the user interface to check the  
393 site for occlusion and test blood glucose.

394 If a participant's CGM reading is >300 mg/dL for more than 60 minutes or is  $\geq$ 400 mg/dL at any point,  
395 the participant will be instructed to take the following steps:

- 396 • Perform a blood glucose meter check.
- 397 • If the blood glucose is >300 mg/dL, check for blood ketones with the study ketone meter.
- 398 • If the ketone level is  $\geq$  0.6 mmol/L (or  $\geq$  2.5 mmol/L at any time), take correction insulin, change  
399 insulin (pump) infusion site and contact study staff. Continue to monitor their glucose and blood  
400 ketone levels until they return to normoglycemia and ketones are < 0.6 mmol/l.
- 401 • If ketones are <0.6 mmol/l, they will be advised to continue to monitor their glucose until it  
402 returns to normoglycemia and to repeat the ketone measurement in 90 minutes if necessary
- 403 • If correction insulin is administered via insulin syringe, turn Control-IQ off for four hours and  
404 until glucose level has returned to <180 mg/dL.

405 **3.1.4 Participant Reporting of Infusion Set Insertion Reactions**

406 Participants will receive a weekly contact (phone, email and/or text message) to assess any issues related  
407 to their current infusion site.

408 Participants will be instructed to take a photo at time of removal of the first 2 infusion sets and  
409 subsequently photo at the time of removal only if there is redness on skin when the infusion set is  
410 removed. Additional photos may be needed if during a virtual visit, video is not available.

411 **3.1.5 Adjustments in Insulin Pump Settings**

412 Insulin and glucose data from the Lead-in Period will be reviewed and the site investigator may adjust  

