### 707 **6.2.4 Hyperglycemic/Ketotic Events**

708 Hyperglycemia not associated with an Adverse Device Effect or discontinuation of the study device or  
709 study drug is only reportable as an adverse event when one of the following criteria is met:

- 710 • the event involved DKA, as defined by the Diabetes Control and Complications Trial (DCCT)  
711 and described below
- 712 • evaluation or treatment was obtained at a health care provider facility for an acute event involving  
713 hyperglycemia or ketosis, or the participant contacted the site and received guidance on how to  
714 manage the hyperglycemia/ketosis
- 715 • blood ketone level  $\geq 1.0$  mmol/L, even if there was no communication with a health care provider  
716 at the time of the event

717 Hyperglycemic events are classified as DKA if the following are present:

- 718 • Symptoms such as polyuria, polydipsia, nausea, or vomiting;
- 719 • Serum ketones  $>1.5$  mmol/L or large/moderate urine ketones;
- 720 • Either arterial blood pH  $<7.30$  or venous pH  $<7.24$  or serum bicarbonate (or CO2)  $<15$ ; and
- 721 • Treatment provided in a health care facility

722 When a hyperglycemia/ketotic event qualifies as an SAE as defined in section 6.2.1, a Hyperglycemia/  
723 DKA Form should be completed in addition to the Adverse Event Form. Events meeting DKA criteria  
724 should be considered to be serious adverse events with respect to reporting requirements. Hyperglycemia  
725 events not meeting criteria for DKA generally will not be considered as serious adverse events unless one  
726 of the SAE criteria in section 6.2.1 is met.

727 When a hyperglycemia/DKA event occurs during use of a study device, it generally will be considered to  
728 be unrelated to the device (per section 6.2.6) if the device functioned as intended and there does not  
729 appear to be a flaw in how the device is intended to function.

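### Meal-challenge item 5 can bar a bolus when section 3.1.3 orders correction insulin for raised ketones, and neither rule is given precedence

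*Protocol*

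**What the plan says.** Protocol section 5.1.1 sets the rules for each meal challenge: one during the Humalog lead-in and three on Lyumjev. Two of the four are eaten with no meal bolus. The meal holds at least 50 g of carbohydrate, and the starting glucose must lie between 70 and 200 mg/dL. Item 5 reads "Not give an additional bolus for up to 3 hours after the meal challenge, unless BG is above 300" and continues "mg/dL for more than 1 hour, or symptoms of hyperglycemia develop". Those are its only two exceptions.

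Section 3.1.3 sets the general response to high glucose. It starts when a participant's "CGM reading is >300 mg/dL for more than 60 minutes or is" at or above 400 mg/dL at any point. The participant then checks the meter and, if it reads above 300, tests blood ketones. The step for ketones of at least 0.6 mmol/L (with a parenthesis ending "mmol/L at any time), take correction insulin, change" and then the infusion site) also calls for contact with study staff. Below 0.6 the instruction is different: "If ketones are <0.6 mmol/l, they will be advised to continue to monitor their glucose until it" is back to normal.

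No sentence ranks the two sections. Section 5.1.1 asks caregivers of pediatric participants to observe the safety guidelines in addition to the challenge rules. It has no matching sentence for adults.

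**The concern.** Item 5 repeats one of the two triggers in section 3.1.3, roughly an hour above 300 mg/dL, and leaves out the other: 400 mg/dL at any point, followed by a ketone test. A participant who reaches 400 quickly and finds raised ketones can therefore be told to take insulin by one section and not to bolus by the other.

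The ketone result matters most in the no-bolus challenges. High glucose is expected after such a meal, so glucose alone cannot reveal a failed infusion set. Section 1.3.1.4 links ketonemia to reduced or suspended delivery and to a pump or set that is not working. Section 6.2.4 treats raised ketones as worth recording in their own right: a hyperglycemic event with ketones of at least 1.0 "mmol/L, even if there was no communication with a health care provider" is reportable, with no condition on symptoms or duration. What is at stake is a short delay in rescue insulin for a participant who follows item 5 to the letter.

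**Working it through.** The plan gives no figure for this point, so the check is a comparison of conditions, followed by a short timing calculation.

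**Assumption.** Item 5 speaks of BG and section 3.1.3 of CGM. I treat time above 300 mg/dL as one clock for both.

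**The two rules, within 3 hours of the challenge, meter above 300 mg/dL:**

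| State | Section 3.1.3 | Item 5 | Result |
|---|---|---|---|
| Above 300 for more than 1 hour, ketones at least 0.6 | Correction insulin | Bolus allowed | Agree |
| CGM at least 400, no more than 1 hour above 300, no symptoms, ketones below 0.6 | Monitor only | Bolus barred | No conflict |
| CGM at least 400, no more than 1 hour above 300, no symptoms, ketones at least 0.6 | Correction insulin | Bolus barred | **Conflict** |
| CGM at least 400, symptoms present, ketones at least 0.6 | Correction insulin | Bolus allowed | Agree |

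Only the third row conflicts.

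**How fast glucose must rise.** The third row needs a climb from 300 to 400 within 60 minutes, so the mean rise must be at least (400 − 300)/60 = 1.67 mg/dL per minute.

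**How long the conflict can last.** At a constant rise r, CGM reaches 400 after 100/r minutes above 300, and item 5 releases the bolus after 60. The longest window is 60 − 100/r minutes, less any time d spent on the meter and ketone tests. The rates and test times are illustrative; the documents give none.

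| r (mg/dL/min) | d = 0 | d = 5 | d = 10 |
|---|---|---|---|
| 1.67 | 0 | none | none |
| 2 | 60 − 50 = 10 | 5 | 0 |
| 3 | 60 − 33.3 = 26.7 | 21.7 | 16.7 |
| 4 | 60 − 25 = 35 | 30 | 25 |

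**Whether it falls inside the 180 minutes.** Counting from the start of the challenge at glucose G, CGM reaches 400 at (400 − G)/r minutes.
- From 200 mg/dL this is 200/2 = 100, 200/3 = 66.7 and 200/4 = 50 minutes at the three higher rates.
- From 70 mg/dL it is 330/2 = 165, 330/3 = 110 and 330/4 = 82.5 minutes.
- From 70 mg/dL at less than 330/180 = 1.83 mg/dL per minute, CGM reaches 400 only after 180 minutes and no conflict arises.

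So the state can be reached within the ban, but not at every qualifying rate and starting value. These figures time glucose only. They do not say how often ketones would be at 0.6 mmol/L or more in that window, and the documents do not say either.

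**Exposure.** With 160 completers and two no-bolus challenges each, 160 × 2 = 320 no-bolus challenges are planned. That counts opportunities, not expected conflicts.

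**The case against.** The strongest reply is that the two rules concern different things. Item 5 limits an additional bolus so that the challenge stays interpretable, whereas section 3.1.3 prescribes correction insulin as a ketone rescue and foresees a route other than the pump: "If correction insulin is administered via insulin syringe, turn Control-IQ off for four hours and" a glucose condition is met. If ketones rise because a set has failed, the new site and the call to staff come first, and item 5 forbids neither. Staff review procedures within a day before each challenge, and children have a caregiver with them for the 3 hours.

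Much of this stands as a limit on weight. It does not remove the conflict. The syringe is mentioned conditionally, and no text says that an additional bolus excludes a correction dose by either route. Staff are given no rule on which instruction governs. Caregiver presence is stated for pediatric participants only.

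A reader might also infer several stronger points that the documents do not support:
- *Every CGM value of 400 or more produces a conflict.* It does not; below 0.6 mmol/L section 3.1.3 orders monitoring only.
- *Ketones of 2.5 mmol/L or more are a separate trigger at any glucose level.* That wording is a parenthesis inside a step reached after a meter reading above 300, so this reading is strained.
- *Lead-in participants lack the hyperglycemia instructions.* Section 3.1.1, on Lyumjev training, says "The participant will be given a User Guide as a reference as well as Hypoglycemia and Hyperglycemia" Guidelines, but not that they are issued only then. Section 2.5 includes ketone-meter training at lead-in, and the Protocol Summary refers to a study safety plan with meters used throughout. A gap is not shown.
- *The 1.0 mmol/L threshold in section 6.2.4 shows that insulin is needed sooner.* It is a reporting criterion, not a treatment threshold.

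**Conclusion.** Wrong as written, and minor. In one defined state (CGM at least 400 mg/dL, meter above 300, ketones at least 0.6 mmol/L, no more than an hour above 300, no symptoms) section 3.1.3 orders correction insulin, both exceptions in item 5 are false, and neither section is given precedence.

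The existence of that state follows from the text, given one clock for CGM and BG and a reading of an additional bolus that includes a correction dose. Its size is not established. It is narrow, probably rare and brief: at illustrative rises of 2 to 4 mg/dL per minute it lasts at most 10 to 35 minutes, and less once testing time is taken off. The likely harm is small, because the step that orders insulin also sends the participant to staff and automated delivery continues. No endpoint, comparison or other statistical result is affected.

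**What to change.** Add one clause to the exceptions in item 5, for all four meal challenges: *or section 3.1.3 calls for correction insulin, in which case section 3.1.3 takes precedence*.

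Add no separate exception for CGM of 400 or more, since item 5 should go on barring a bolus when ketones are below 0.6. Add no stand-alone ketone trigger either: lifting the ban at 0.6 mmol/L regardless of glucose would permit a bolus with the meter at or below 300, where the 0.6 step in section 3.1.3 does not apply. Pointing to section 3.1.3 avoids both problems.

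The cost is one clause in the protocol and in the participant instructions, with IRB approval as for any amendment (section 10.2), and no new visits or tests. A few challenges may then contain rescue insulin, including some in the no-bolus comparison of lead-in with treatment (SAP section 8.4), but item 5's existing exceptions already allow that. SAP version 4.0 records enrollment and follow-up as complete, so the change now serves the protocol text and any later study that reuses this challenge.
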